2. SYNOPSIS

TITLE: A multicenter, non-interventional study to evaluate physical

activity, bleeding incidence and health related quality of life, in patients with haemophilia A without inhibitors receiving

standard of care treatment

PROTOCOL NUMBER: ML40983

VERSION NUMBER: 3.0

DATE OF SYNOPSIS: 26 Jul 2019

STUDIED MEDICINAL None

PRODUCT:

INDICATION Haemophilia A without inhibitors

STUDIED INITIATOR: Roche S.p.A.

[name]

MAIN AUTHOR:

Research Question and Objectives

Objectives

The primary objective for this study is to document physical activity, particularly in terms of active minutes, steps count and Metabolic Equivalent of Tasks (MET) over the 12 months period, by age categories (12-17, 18-30 and 31-50 years) in patients with haemophilia A without inhibitors receiving standard of care treatment.

The secondary objectives for this study are as follows:

- To document physical activity, particularly in terms of active minutes, by ages categories (12-17, 18-30 and 31-50 years), by type of physical activity and by intensity (as per fitness tracker default categorization);
- To describe the observed population in terms of:
 - Number of patients who are adherent to World Health Organization (WHO) Guidelines (i.e., Global Recommendations on Physical Activity for Health) for the definition of physical activity;
 - Number and type of bleeds occurring during routine clinical practice and reported at any occurrence via the electronic Patient-Reported Outcome (ePRO) application;
 - Treatment regimen for haemophilia A (prophylaxis, preventative treatment before physical activity, treatment for any episode of bleeds), in terms of type of regimen (ondemand vs. prophylaxis), product used and dose;
 - Health-Related Quality of Life (HRQoL) and health status (evaluated at baseline, every three months, and at the end of the study) reported during routine clinical practice, measured using the European Quality of Life-5 Dimensions (EQ-5D-5L) score (adults/adolescents);
 - Dose and frequency of concomitant medications taken to control pain (e.g., nonsteroidal anti-inflammatory drugs [NSAIDs], painkillers);

- Joint health status of enrolled patients, based on Haemophilia Joint Health Score (HJHS) questionnaire (evaluated at baseline, at six months, and at the end of the study);
- Body Mass Index (BMI) evaluated at baseline and every three months;

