Descriptive statistics will be provided in summary tables according to the type of the variable. Continuous variables will be summarized by using number of cases, mean, and standard deviation, median, quartiles and range (i.e. minimum and maximum). Categorical variables will be summarized by using frequency and percent distribution.

Primary variables (*i.e.*, daily evaluations of active minutes, step counts and METs) will be analyzed over the 12 months' observational period by means of descriptive statistics (e.g. weekly/monthly). The 95% confidence interval (CI) of the mean will be also presented. Moreover, results will be also shown graphically, if deemed necessary.

Analyses on primary variables will be conducted on patients with established valid measurements from the fitness tracker.

A sensitivity analysis could also be performed evaluating the relationship of primary variables with baseline, demographic or other clinically relevant variables which will be detailed and described in the SAP.

Secondary variables will be summarized by using descriptive statistics as indicated in general methodology section, according to the type of variable analyzed, at any given time point (where applicable). The 95% CI of the mean change could be also presented.

Particularly, the proportion of patients who will meet WHO recommendations for physical activity will be summarized using descriptive statistics and 95% CIs as well.

The same analysis will be performed on active/sedentary patients and severe/moderate patients.

A further exploratory analysis will be performed in patients that will start treatment with any newly approved drugs during the study. An intra-patients comparison will be performed on pre and post treatment start primary and secondary variables evaluations, through means of descriptive statistics.

Due to the exploratory nature of this study, no adjustment for multiplicity will be made.

Study Size/Determination of Sample Size

Given the exploratory nature and the objectives of this non-interventional study, rather than testing a formal hypothesis, a justification based on epidemiologic data from the Italian registry of congenital bleeding disorders (*Giampaolo et al. 2017*) was considered more appropriate than a power calculation in the traditional fashion or using an estimation approach through the precision of confidence intervals.

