Furthermore, this study will also evaluate joint health status in the main joints by means of the Haemophilia Joint Health Score (HJHS) questionnaire.

New upcoming therapies for haemophilia A will likely continue to change clinical practice. Ranging from new extended half-life to nonfactor products and gene therapy, these innovative approaches have the potential to enhance the standard of care by decreasing infusion frequency to increase compliance, promoting prophylaxis, easing route of administration, ensuring in some cases also more efficacy reducing the risk of bleeds, and in particular also the number of target joint bleeds, all characteristics that could have a significant impact on physical activities and quality of life. Therefore, for patients that will start treatment with any newly approved therapy, during the observational period (in case the drugs will be approved for the treatment of Haemophilia A without inhibitors against FVIII during the observational period) the study will also document the effect of the start of the new therapies compared with the previous standard of care.

In the context of this study, newly approved drugs are considered all those newly approved during the course of the study and commercially available for prophylaxis treatment in patients with Haemophilia A without inhibitors.

Rationale for Electronic Patient Reported Outcomes with bring-your-own-device (BYOD)

Advances in technology have significantly increased electronic PRO (ePRO) data collection capabilities and options in clinical trials, observational studies, and registries (*Jones et al. 2013; Wysham, Wolf, Samsa, Abernethy, & LeBlanc, 2017*). ePROs provide more accurate and complete data, improve protocol compliance, prevent secondary data entry errors, pose less administrative burden and have high respondent acceptance (*Coons et al. 2015*).

In order to make study participation more engaging and convenient, an approach that leverages patients' own devices to enable the collection of self-report data ("Bring Your Own Device" [BYOD]) has been previously used. There is strong evidence supporting equivalence between BYOD, paper and a provisioned electronic device to administer PROs composed of typical response scale types (visual analogue, verbal response, and numeric response scales). This equivalence is maintained when migrating between these different formats (*Byrom, Doll, et al., 2018; Byrom, Gwaltney, Slagle, Gnanasakthy, & Muehlhausen, 2018*).

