6.7.1 Analyses

Primary variables (*i.e.*, daily evaluations of active minutes, steps count, METs) will be analysed over the 12-18 months' observational period by means of descriptive statistics (e.g. weekly/monthly). The 95% confidence interval (CI) of the mean will be also presented.

Moreover, results will be also shown graphically, if deemed necessary.

Analyses of primary variables will be conducted on patients with established valid measurements from the fitness tracker.

A sensitivity analysis could also be performed evaluating the relationship of primary variables with baseline, demographic or other clinically relevant variables, which will be detailed and described in the SAP.

Secondary variables will be summarized by using descriptive statistics as indicated in general methodology section, according to the type of variable analyzed, at any given time point (where applicable). The 95% CI of the mean change could be also presented.

Particularly, the proportion of patients who will meet WHO recommendations for physical activity will be summarized using descriptive statistics and 95% CIs as well.

The same analysis will be performed on active/sedentary patients and severe/moderate patients.

A further exploratory analysis will be performed in patients that will start treatment with any newly approved drugs during the study. An intra-patient comparison will be performed on pre and post treatment start primary and secondary variables evaluations.

Due to the exploratory nature of this study, no adjustment for multiplicity will be made.

6.7.2 Interim and Final Analyses and Timing of Analyses

One interim analysis is planned, when all enrolled patients have completed 6 months of observation, to have a preliminary evaluation of results and to check if any adjustment in terms of number of required patients or in terms of study procedures may be necessary.

Once the study database is considered clean and before database lock, a data review meeting might be performed. During this meeting the study data will be reviewed to identify potential issues and document decisions taken to address them before the database is locked and the analysis of the data starts. Details of this analysis will be provided in the SAP.

A final analysis will be carried out at the end of study, *i.e.* all patients enrolled and followed up (with no limitations in the period of follow-up) will be included in the data analysis.

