**Table 1: Study scheme**

		Observational period	
		Standard observational period for all observed patients	Prolonged observational period if patients start newly approved drugs between Month 6 and Month 12
Baseline	Month 0 to Month 12	6 months after the start of new therapy (e.g., max observation period of 18 months if patients start the newly approved drugs during the last month of standard observational period).	

The entire observational period will last 12 months. Patients that will start treatment with any newly approved drugs between Month 6 and Month 12 will complete a 6-month observational period after the switch, and therefore the entire observational period in these patients may be prolonged up to a maximum of 18 months. In the context of this study, newly approved drugs are considered all those newly approved

during the study and commercially available for prophylaxis treatment in patients with Haemophilia A without inhibitors.

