## **4. STATISTICAL METHODS**

Appropriate descriptive statistics will be produced, according to the variable. For continuous data n, mean, standard deviation (SD), median, I and III quartile, and range (minimum and maximum) will be presented. For categorical data, frequency distributions and percentages will be presented.

Unless otherwise specified, hypothesis testing (exploratory in nature) will be carried out at the alpha = 0.050 level (two-sided). For all inferential analyses, the p-values will be rounded to three decimal places. Due to the exploratory nature of this study, no adjustment for multiplicity will be made.

Any unplanned analyses as well as deviations from the original SAP will be clearly documented in the Clinical Study Report.

All the data collected and derived in the study will be presented in subject data listings.

With reference to the ePROs and physical activity data (i.e. all data derived from ePRO app and the fitness tracker), only data collected between the informed consent date and Date of patient completion or withdrawal (extremes included) will be analyzed. For the interim analysis, the minimum between Date of patient completion or withdrawal and the cut-off date will be considered as upper bound.

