## **4.4 EFFICACY ANALYSIS**

#### **4.4.1 Co-primary Endpoints**

All the co-primary endpoints presented in Section 2.2.1, i.e.:

- active minutes:
  - heart zone minutes (overall, fat-burn minutes, cardio minutes, peak minutes)
  - active zone minutes (overall, lightly active minutes, fairly active minutes, very active minutes)
  - MVPA minutes
- METs
- number of steps

will be summarized at subject level as median per day (i.e. the median of each parameter will be calculated by using all the valid days collected during the observational period for each subject). Each parameter, derived as median per day at subject level, will be analyzed by means of descriptive statistics as described in Section 4. The 95% confidence interval for the mean will be also displayed.

The statistics will be shown overall and by age groups (12-17, 18-30 and 31-50). The comparison among the age groups will be performed by means of a one-way ANOVA or, if assumptions of normality is not confirmed (by a visual inspection: histogram and qq-plot), by means of a Kruskal-Wallis test.

Daily physical activity will also be summarized:

- by start of any newly approved drug for haemophilia (see Section 4.4.4 for subgroup definition).
- by COVID-19 period on the EVL population (see Section 4.4.4 for subgroup definition).
- by month through the entire observational period on the EVL to observe the impact of COVID-19.

Data will be summarized at subject level considering data collected in each period above-mentioned.

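### The primary window is 12 months in the objective and synopses but 12-18 months in protocol 6.7.1, and the SAP's all-days median therefore takes in post-switch days beyond month 12

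*Protocol*

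**What the plan says.** The protocol synopsis states the primary objective as documenting active minutes, steps and METs over 12 months, by three age groups, "in patients with haemophilia A without inhibitors receiving standard of care treatment". Protocol 5.2.1 keeps the 12 months but drops the words about standard of care. The Data Analysis part of the protocol synopsis, repeated in SAP Appendix 1, says the primary variables "will be analyzed over the 12 months' observational period by means of descriptive statistics".

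Protocol 6.7.1 differs: the same variables "will be analysed over the 12-18 months' observational period by means of descriptive statistics". Protocol 6.7.2 adds that the final analysis takes in all follow-up without limit of duration.

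SAP 4.4.1 follows the longer window: "the median of each parameter will be calculated by using all the valid days collected during the observational period for each subject". The section on the study scheme (SAP Table 1) says that for patients starting a newly approved drug between months 6 and 12, "the entire observational period in these patients may be prolonged up to a maximum of 18 months". The only date limit on tracker data is in SAP section 4: "only data collected between the informed consent date and Date of patient completion or withdrawal (extremes included) will be analyzed".

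SAP 4.4.1 also plans summaries by start of a newly approved drug and by month. SAP 4.4.4 splits switchers into before and after the switch, and SAP 4.1.4 defines a SWITCH population. These come on top of the overall and age-group summaries. SAP 4.4.3 plans no sensitivity analysis.

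**The concern.** The documents give two different windows for the primary analysis, and the SAP implements the one that does not match the objective. The extra months are not a neutral extension: the schedule grants them only to patients who have changed treatment. Protocol 6.1.2 presents that follow-up as a comparison, in which "the study will also document the effect of the start of the new therapies compared with the previous standard of care", and both documents list it as an exploratory objective. Days collected for the exploratory comparison therefore feed the primary number.

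This is a descriptive study, so its main product is a clear statement of what the primary figure describes. As written, the overall mean, the age-group means, their confidence intervals and the ANOVA or Kruskal-Wallis comparison describe 12 months for most patients and up to 18 months, partly on a new drug, for some. If switching differs by age, the age comparison is affected too.

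**Working it through.** **The plan's own figure.** The longest follow-up is a switch at month 12 plus 6 months: 12 + 6 = 18 months, as stated. The SAP 2.3 precision also checks: at 150 patients the 80% bound on the half-width is 0.169 SD, against 0.17 stated. It is not at issue here.

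**Inputs.** Protocol 6.1.1 and 6.1.2: follow-up is 12 months for non-switchers and for switches in the first 6 months; for a switch at month m between 6 and 12 it runs to m + 6. Equal wear before and after the switch is assumed.

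**Formulas.** End of follow-up = max(12, m + 6). Out-of-window months = end − 12. Post-switch share on all days = (end − m)/end. Post-switch share after a month-12 cut = (12 − m)/12.

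**Size.** The documents give no number of switchers and no activity change. Assume that 20% of patients switch, all at month m, and that the share of a post-switch change D showing in a switcher's median equals the share of post-switch days. The mean then moves by 0.20 × share × D.

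| Switch at month | End | Out-of-window months | Post-switch share, all days | Post-switch share, cut at 12 | Mean shift, all days | Mean shift, cut at 12 |
|---|---|---|---|---|---|---|
| 1 | 12 | 0 | 11/12 = 92% | 92% | 0.18D | 0.18D |
| 3 | 12 | 0 | 9/12 = 75% | 75% | 0.15D | 0.15D |
| 6 | 12 | 0 | 6/12 = 50% | 50% | 0.10D | 0.10D |
| 9 | 15 | 3 (20%) | 6/15 = 40% | 3/12 = 25% | 0.08D | 0.05D |
| 12 | 18 | 6 (33%) | 6/18 = 33% | 0% | 0.07D | 0 |

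The window conflict alone accounts for the difference between the last two columns: nothing for switches by month 6, 0.03D at month 9, 0.07D at month 12. The larger shifts for early switches come from days inside the 12 months, which a month-12 cut does not touch.

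**Check on the proportionality assumption.** Model a switcher's days as a two-part normal mixture with D of 0.25 to 1.0 day-level SD. On all days the median moves by 0.08 to 0.32 SD (month 12), 0.13 to 0.50 (month 6) and 0.19 to 0.77 (month 3), close to share × D. With 5% to 30% switchers the mean of medians moves by about 0.004 to 0.23 day-level SD. This is a within-patient scale, so it should not be set against the SAP's 0.17 SD, which is between patients.

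**The case against.** The strongest defence has four parts.

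- **Protocol 6.7.1 does not itself pool.** It mentions weekly or monthly descriptives as examples, and in a monthly table months 13-18 would be separate rows. That is fair: the pooling comes from the per-patient median in SAP 4.4.1. The two windows still conflict, and monthly rows past month 12 would by schedule hold switchers only.
- **Pre-switch activity is already reported.** The before/after summaries and the SWITCH population do give it, for switchers. They do not take any day out of the overall and age-group results.
- **Longer follow-up gives no extra weight.** Correct: each patient contributes one median, and patients who switch in the first 6 months stay only 12 months. The issue is which days form the median.
- **Days after a switch within months 0-12 may belong in the primary estimate.** A reader might infer that all post-switch days are contamination and that the primary analysis must be censored at the switch. The documents do not compel that. Protocol 5.2.1 omits the standard-of-care phrase; in the synopsis it can be read as describing who is enrolled; and protocol 4.1 says new products may enhance the standard of care. Protocol 6.1.2 points the other way by setting new therapies against previous care, but it does not settle the matter.

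The last part stands, and it limits the point to the window beyond month 12, with censoring at the switch as an added table.

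**Conclusion.** The point holds for the window. The objective and both synopses say 12 months; protocol 6.7.1 and SAP 4.4.1 do not keep to it. The scheduled excess consists wholly of post-switch days, up to 6 of a switcher's 18 months. A late final visit, which the flexible visit windows allow, could also add some days past month 12 for a non-switcher.

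The effect on the reported mean runs from negligible to material and cannot be fixed from the documents. With 20% switchers (assumed) and the proportionality above, pooling all days moves the mean by about 0.07D for switches at month 12 to 0.18D for switches at month 1. Only the part beyond month 12 departs from the stated window. Whether the rest is an error depends on how standard of care is read, which the plan should state. The matter should be corrected, but it does not undermine the study.

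**What to change.** 1. In SAP 4.4.1, compute the primary per-patient median on valid days from baseline to the earlier of day 365 and end of participation. Align protocol 6.7.1 with the synopsis.
2. Use days from month 12 to month 18 only in the SWITCH analysis.
3. Add an overall and age-group table that also stops on the day before the first dose of a newly approved drug, with the number of pre-switch valid days per patient. It is needed because the month-12 cut still leaves 75%, 50% and 25% post-switch days for switches at months 3, 6 and 9.
4. State that the 180-day exposure and 50% compliance rules in SAP 4.1.2 are applied to the month 0-12 window, so that nobody qualifies on days the primary median does not use.
5. Say whether the activity-type and sleep analyses, which SAP 4.4.2 defines by reference to 4.4.1, take the same window.

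**Cost.** A few sentences, a date filter and one extra table; the start date of the new drug is already collected on the medications form. Late switchers lose up to a third of their days from the primary median, and a few patients might lose Evaluable status. In the added table, early switchers rest on short pre-switch windows (about one month for a switch at month 1), possibly in a single season or a lockdown period, so it should be read as supportive.

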6.7.3 Determination of Sample size

Given the exploratory nature and the objectives of this non-interventional study, rather than testing a formal hypothesis, a justification based on epidemiologic data from the Italian registry of congenital bleeding disorders (*Giampaolo et al. 2017*) was considered more appropriate than a power calculation in the traditional fashion or using an estimation approach through the precision of confidence intervals.

Based on data collected from the 54 Hemophilia Treatment Centers, members of the Italian Association of Hemophilia Centres (AICE), it is estimated that the planned number of participants in this study will represent approximately 10-15% of patients with Haemophilia A in Italy in the same age range and category of severity planned for this study. The total sample

Roche S.p.A

size planned is approximately 150 patients overall, 125 patients with severe Haemophilia A and 25 patients with moderate Haemophilia A.

6.8 STUDY DOCUMENTATION, MONITORING, AND ADMINISTRATION

6.8.1 Study Documentation

The physician must maintain adequate and accurate records to enable the conduct of the study to be fully documented, including but not limited to the protocol, protocol amendments, Informed Consent Forms, and documentation of EC and governmental approval/notification. In addition, at the end of the study, the physician will receive the patient data, which include an audit trail containing a complete record of all changes to the data.

6.8.2 Site Audits and Inspections

Site visits could be conducted by the Sponsor or an authorized representative for audit of study data entered in the eCRF and patients' medical records.

The physician will also permit national (Italian or foreign countries) and local health authorities to inspect facilities and records relevant to this study.

In case the site will receive a notice for an inspection from a Regulatory Authority, the Investigator will promptly inform the Sponsor.

6.8.3 Use of Site Computerized Systems

In this study, physical activity will be measured by wearing a study device, in a continuative manner, during study participation. Data collected on physical activity will be transferred to a database. Investigators will access remotely the database, via website, reviewing data input by patients and physical activity adherence and reports.

Data collection will be performed by the patients through a dedicated ePRO: an application that runs on the patient's own device (BYOD approach) for data collection and management of subjects. Patients will input data electronically as required by the study (bleeds, bleeds treatment, HRQoL, VAS).

When clinical observations are entered directly into a computerized medical record system (*i.e.*, in lieu of original hardcopy records), the electronic record can serve as the source document if the system has been validated in accordance with health authority requirements pertaining to computerized systems used in clinical research. An acceptable computerized data collection system allows preservation of the original entry of data. If original data are modified, the system should maintain a viewable audit trail that shows the original data as well as the reason for the change, name of the person making the change, and date of the change.

